Official Title

Study of Tretinoin Capsules in Combination With Azacitidine and Venetoclax in Treatment Naïve Participants With Acute Myeloid Leukemia

NCT Number NA

Document Time February 2, 2025

Subject Number: Version Number: 1.0

Study of Tretinoin Capsules in Combination With Azacitidine and Venetoclax in Treatment Naïve Participants With Acute Myeloid Leukemia

I.Research protocol

The experimental group will receive a combination therapy of all-trans retinoic acid (ATRA), azacitidine, and venetoclax, while the control group will receive a combination therapy of daunorubicin and cytarabine. All patients need to complete two cycle of induction therapy. After two cycle of induction therapy the patients who are willing to receive bone marrow transplantation can be treated with a bone marrow transplant, and the patients who refuse the bone marrow transplantation can treated with consolidation therapy followed by connective maintenance therapy.

(1) Experimental group:Inductive therapy: AZA 75mg/m² per day for days 1-7 and venetoclax 100mg orally for day 1, 200mg orally for day 2, 300mg orally for day3-5, 400mg orally for day 6-9,ATRA 45mg/m² for day 11-28,every 28 days for up to 2 cycles or progression; Consolidate therapy:AZA 75mg/m² per day for days 1-7 and venetoclax 100mg orally for day 1, 200mg orally for day 2, 300mg orally for day3-5, 400mg orally for day6-9,ATRA 45mg/m² for day 11-28,every 28 days for up to 2 cycles or progression; Maintenance therapy:ATRA 45mg/m² for d1-21 every 28 days,AZA 70mg/m² per day for days 1-7.Once per month for 4 doses, followed by once every 3 months, commencing concurrently with azacitidine untill progression; (2) Control group:Inductive therapy: Daunorubicin: 60 mg/m² for day 1-3, Cytarabine: 100 mg/m² for day 1-7,every 28 days for up to 2 cycles or progression; Consolidate therapy:A chemotherapy regimen with intermediate-dose cytarabine alone or in combination with anthracycline drugs (cytarabine 1.5-2g/m²),every 28 days for up to 2 cycles or progression; Maintenance therapy:AZA 70mg/m² per day for days 1-7.Once per month for 4 doses, followed by once every 3 months, commencing concurrently with azacitidine untill progression;

II. Study procedure and time frame

The efficacy was assessed within 2 years after treatment, and the assessment indexes included composite complete response (CRc), the overall response rate (ORR), MRD, rate of transfusion independence and overall survival (OS).

III. Conventional treatment plan outside the study

Participants may utilize other "3+7" regimens combining mitoxantrone/idarubicin with cytarabine, or the FLAG-IDA protocol, in addition to this study. Symptoms may be alleviated and the disease may respond to treatment. However, this is often accompanied by side effects such as nausea, vomiting, hair loss, and oral mucositis, which suppress bone marrow function leading to a decrease in white blood cells, red blood cells, and platelets, increasing the risks of infection, anemia, and bleeding. There is also potential for damage to organs such as the liver, kidneys, and heart. Additionally, there may be the development of resistance to certain chemotherapy drugs,

leading to a decrease in therapeutic efficacy or disease non-response. It is not guaranteed to be more effective than existing treatments.

IV. Clinical data processing and confidentiality of clinical research data

The information and data recorded by the subjects participating in the study will be kept strictly confidential and will not be disclosed, and if the study results are published, the subjects identity information will also be kept confidential. At the same time, conduct regular patient follow - up, data detection, and complete data entry. After all the data have been collected, use SPSS 23.0 statistical software for data processing and analysis.

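### The maintenance schedule sentence in both arms does not say which drug it governs, so maintenance azacitidine may be given at different intervals

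*Protocol*

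**What the plan says.** Section I of the protocol sets out maintenance in item (1) for the experimental arm and item (2) for the control arm.

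- Experimental arm: "ATRA 45mg/m² for d1-21 every 28 days,AZA 70mg/m² per day for days 1-7.Once per month for 4 doses". The 28-day interval stands next to ATRA. Azacitidine follows after a comma, and the schedule sentence begins after a full stop.
- Control arm: "Maintenance therapy:AZA 70mg/m² per day for days 1-7.Once per month for 4 doses". Azacitidine is the only drug named.
- Both arms then carry the same schedule sentence, which reads in full: "Once per month for 4 doses, followed by once every 3 months, commencing concurrently with azacitidine untill progression". It has no grammatical subject.

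Induction and consolidation are written differently. Experimental induction and consolidation both end "ATRA 45mg/m² for day 11-28,every 28 days for up to 2 cycles or progression", and control induction ends "Cytarabine: 100 mg/m² for day 1-7,every 28 days for up to 2 cycles or progression". Control consolidation closes with the same interval wording.

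Maintenance does not reach everyone. After two induction cycles patients may have a transplant, while "the patients who refuse the bone marrow transplantation can treated with consolidation therapy followed by connective maintenance therapy". Section II lists overall survival among the indexes and says that "The efficacy was assessed within 2 years after treatment".

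**The concern.** A repeat-dosing rule should tell a site which drug is given and when the next course falls. This sentence gives two intervals, a count and a duration, but no drug. Its one reference to a drug, the closing mention of azacitidine, makes matters worse: a schedule that starts alongside azacitidine would ordinarily belong to something other than azacitidine.

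What is at stake is consistent delivery of an active drug after consolidation, in both arms. Section II places overall survival within a two-year assessment, so maintenance can fall inside the assessed period. If sites read the sentence differently, patients assigned to the same arm may receive different amounts of azacitidine. Response assessed after induction is less affected.

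**Working it through.** The document states no figure on this point that could be reproduced. The check is a comparison of readings, followed by a simple count for scale.

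**Step 1. Test each candidate drug against the text.**

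| Drug governed | In favour | Against |
|---|---|---|
| Azacitidine | The sentence follows it directly; it is the only control maintenance drug; in all four induction and consolidation regimens the closing interval governs the regimen before it | Azacitidine would start concurrently with azacitidine; a 7-day course is called a dose; none of the four other closing intervals refers back to a drug by name |
| A further, unnamed drug | Literal sense of starting concurrently with azacitidine | No such drug is named in either arm |
| ATRA | Named in experimental maintenance | Already has its own 28-day schedule; absent from control maintenance, where the same sentence appears |

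The ATRA reading fails. Of the other two, the first is likelier and the second is closer to the literal words. Neither is free of difficulty, and nothing else in the document decides between them.

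**Step 2. What each reading leaves for azacitidine.**

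- If the sentence governs azacitidine, both arms have the same stated schedule: monthly for four, then every three months.
- If it governs another drug, control-arm azacitidine has no repeat interval. In the experimental arm, "Maintenance therapy:ATRA 45mg/m² for d1-21 every 28 days,AZA 70mg/m² per day for days 1-7" has one interval, attached to ATRA, and its reach over azacitidine is open. The ambiguity is therefore not identical in the two arms.

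**Step 3. Illustrative course counts over the first 12 months of maintenance.**

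Assumptions, none of them in the document: maintenance starts on day 0; the window is 365 days; the patient does not progress; each dose means one 7-day course; and, if the sentence does not govern azacitidine, azacitidine repeats monthly or every 28 days.

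- Counting in 28-day units, sentence governs azacitidine: starts on days 0, 28, 56, 84, then every 84 days on 168, 252 and 336. That is 4 + 3 = 7.
- Counting in 28-day units, sentence does not govern azacitidine: starts on days 0, 28, ..., 364. That is 364/28 + 1 = 14, or 13 if the course starting on day 364 is left out because it does not finish by day 365.
- Counting in calendar months, sentence governs azacitidine: starts at months 0, 1, 2, 3, 6 and 9, which is 6.
- Counting in calendar months, sentence does not govern azacitidine: starts at months 0 to 11, which is 12.

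Result: 6-7 against 12-14 courses. Within one convention the ratio is 14/7 = 2.0, 13/7 = 1.9 or 12/6 = 2.0. The first four courses coincide under both readings; the difference arises only after them.

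**The case against.** The strongest reply is that one reading works. The sentence sits directly after azacitidine, nothing else is named in control maintenance, and the protocol habitually puts the interval last. On that reading both arms share one azacitidine schedule and the closing phrase is merely redundant, in a document whose English is loose throughout. Calling a 7-day course a dose adds little to the ambiguity. Much of this stands. A reader might infer that maintenance azacitidine cannot be given uniformly. The document does not support that, because sites that all take the likelier reading can follow it. It supports only that azacitidine may be given differently.

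A second reply is that the higher course counts do not come from the document. That also stands: on the literal reading the control arm has no azacitidine interval, so one has to be supplied. The counts show scale and do not measure an effect on the trial. Carrying them out to two years would need further assumptions, about when the clock in section II starts and about every patient completing four back-to-back cycles, so that is not done here.

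A third reply is that no two stated figures conflict in the control arm, and that in the experimental arm the 28-day interval conflicts with the sentence only if it is also read as covering azacitidine. This is right. The defect is an ambiguous dosing sentence, not a proven contradiction between figures.

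What the replies do not remove is the sentence itself. It appears in the same words in both arms with no sign of redaction, and no other passage resolves it.

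**Conclusion.** The point holds as an ambiguity in a stated dosing rule that should be fixed. The wording supports one likelier reading that can be followed and one literal reading that leaves control-arm azacitidine without an interval and experimental-arm azacitidine with an uncertain one. Under the assumptions listed with the counts, the gap is about twofold in the first year of maintenance.

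Exposure is limited to patients who decline transplant and reach maintenance, and their share is not given. Two stronger conclusions might be drawn and are not supported. The first is that the comparison between arms is biased: the disputed sentence is the same in both arms, and although only the experimental text carries a 28-day interval, no size or direction of effect can be established. The second is that a drug has been left out of the protocol: the literal reading implies one, but the likelier reading needs none.

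Confidence is high that the wording is ambiguous. Whether treatment will in fact differ between sites cannot be known from the document. That azacitidine is the likelier subject is a judgement about the text, not about which schedule is clinically right.

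**What to change.** The sponsor should reconcile the maintenance text in section I, items (1) and (2), so that it:

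- names the drug that the schedule sentence governs;
- states the azacitidine repeat schedule in each arm, including whether the 28-day interval in the experimental arm covers azacitidine;
- says which maintenance drugs the duration until progression applies to.

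The choice of schedule and duration is for the clinical team, and none is proposed here. The cost is protocol wording only, with no extra patients or procedures.

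### Does Section III let enrolled patients receive other 3+7 regimens or FLAG-IDA on top of their assigned treatment?

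*Protocol*

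**What the plan says.** Section III of the protocol carries the heading "Conventional treatment plan outside the study". Its first sentence begins "Participants may utilize other" and goes on to allow 3+7 "regimens combining mitoxantrone/idarubicin with cytarabine, or the FLAG-IDA protocol, in addition to this study". The rest of the section describes possible symptom relief and response, then side effects, marrow suppression, organ damage and drug resistance, and closes by disclaiming any guarantee of better efficacy.

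Section I sets the assigned treatment. "The experimental group will receive a combination therapy of all-trans retinoic acid (ATRA), azacitidine, and venetoclax"; the control group receives daunorubicin with cytarabine. It states that "All patients need to complete two cycle of induction therapy". Patients willing to be transplanted may then be, while "the patients who refuse the bone marrow transplantation can treated with consolidation therapy followed by connective maintenance therapy". In both arms, induction and consolidation run for at most two cycles or until progression, and maintenance runs until progression. The one open choice of chemotherapy is in control-group consolidation, described as a "chemotherapy regimen with intermediate-dose cytarabine alone or in combination with anthracycline drugs".

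Section II lists the outcomes, assessed within 2 years after treatment: composite complete response, overall response rate, MRD, transfusion independence and overall survival.

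**The concern.** Two features of the Section III sentence invite the worry. Its subject is participants, not people who decline, and it places the regimens alongside the study rather than in place of it. It sets no limit on arm, phase, timing or reason.

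A site that took this as a permission could give an experimental-arm patient a mitoxantrone- or idarubicin-based 3+7 regimen. Control induction is daunorubicin on days 1-3 with cytarabine on days 1-7, and Section III speaks of *other* 3+7 regimens, so the document itself places these in the comparator's family. Response, MRD, transfusion independence and survival would then partly reflect treatment outside the assigned regimen, and the protocol states no rule for handling it.

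**Working it through.** No figure in the protocol can be reproduced here; the question is what the text means. Set side by side, its features bear on the two readings as follows.

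| Feature of the text | Alternatives to taking part | Permission for enrolled patients |
|---|---|---|
| Section III heading | Fits | Contradicted |
| Subject and linking phrase of the first sentence | Fits only if loosely worded | Fits |
| Benefits, side effects and no-guarantee text that follows | Fits: this is how options are described to a prospective patient | Gives a site nothing to act on |
| No arm, phase, dose, timing or trigger | Expected | A permission would need them |
| Mentions of mitoxantrone, idarubicin or FLAG-IDA in Section I: 0 | Expected | Unexplained gap |

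Only the second row favours the permission reading. The English is rough throughout, as the quotation from Section I on patients who refuse transplant shows. A linking phrase meant as *other than* would make the whole section coherent. That is an inference, but it requires only one misworded phrase.

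**How far the literal reading would contradict Section I.** Section I requires two induction cycles of all patients, but its regimen descriptions cap each phase at two cycles or progression. It therefore foresees patients leaving assigned treatment at progression, and it says nothing about what they receive afterwards. Use of the Section III regimens after progression would contradict nothing in Section I. A contradiction needs two things together:

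1. the sentence is addressed to enrolled patients; and
2. the regimens are given before progression, during assigned treatment.

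The document states the first only through the disputed sentence and does not state the second at all. The open anthracycline choice in control consolidation does not bear on this: it covers one phase of one arm and does not name FLAG-IDA.

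**Size.** Let fE and fC be the shares of the two arms given such therapy. Only those patients' outcomes can change, so:

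- an arm's rate on a yes/no endpoint moves by at most f in either direction;
- the between-arm difference moves by at most fE + fC.

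On the alternatives reading fE = fC = 0, and the bound is 0 + 0 = 0. On the literal reading the document gives no value of f. Assumed shares of 5%, 10% or 20% in one arm give at most 5, 10 or 20 points. The same shares in both arms give at most 10, 20 or 40 points, and only if every affected outcome moves in the opposite direction in the two arms. This bound holds for any trial. It does not cover overall survival as a time-to-event outcome, and it is no evidence about what would happen in this trial.

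**The case for a change.** The best case for a change is that a likely intention is not a stated one. The operative sentence says something different from its heading, and no other sentence decides between them. Section I is silent after progression, and Section III is the only place that names other anti-leukaemia therapy, so a site could turn to it for an enrolled patient. Which treatments enrolled patients may receive is a protocol matter that an SAP cannot settle. Rewording costs one sentence, and if enrolled patients may have these regimens, a recorded start date and a rule counting responses only before it would protect the endpoints.

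Part of this stands. The sentence is badly worded, and the sponsor should say which meaning is intended. The rest does not lead to a change in the plan. The route through progression is the one on which Section I is not contradicted. Counting responses only before other therapy is one defensible way to handle an intercurrent event; following all patients regardless is another. That choice commonly sits in the SAP, which is not shown, so its absence from the protocol is no defect.

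**Conclusion.** No change to the design, endpoints or analysis follows. What remains is a wording slip: the heading of Section III and its first sentence point in different directions, and the sentence read literally does not sit with the regimens assigned in Section I. The sponsor should reconcile these passages; which treatment rule is intended is for the sponsor to state.

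On the more natural reading, the effect on every endpoint is zero. On the literal reading, neither size nor direction can be derived from the document. The conclusion rests on the heading and the descriptive text carrying more weight than one linking phrase, and on the SAP, if one exists, dealing with non-protocol therapy in the usual way. I am confident that the sentence is loosely worded. The document gives no ground for claiming that the comparison is harmed.
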